Unless otherwise noted, baseline values will be those assessments obtained pre-dose within the closest proximity to the first dose.

Safety Assessments will be performed at specified timepoints per the SOA and will include the following:

- Vital signs: Resting HR, seated or semi-supine (same position each time is preferred) systolic/diastolic BP, RR, and temperature
- Clinical laboratory measurements (e.g., biochemistry, hematology, cardiac troponin, lipids, coagulation, FSH, urine pregnancy test [women of childbearing potential {WOCBP}], urine cotinine, and urinalysis)
- Resting ECG measurements (measured after patient is supine or semi-supine [same position each time is preferred] for at least 3 minutes)
- At each visit, patients will be asked about concomitant medications/therapy and will be instructed to volunteer any information regarding AEs and serious adverse events (SAEs) that they may have experienced. Any known untoward event that occurs beyond the AE reporting period that the Investigator(s) considers an SAE and possibly related to study treatment will be reported to the Sponsor

- 90-day, post-last dose follow-up phone call to assess for pregnancy occurrence
- Physical examination (symptom directed as described in the SOA)
- Pulmonary Function Testing including spirometry (including VC, FVC, FEV₁, FEV₁/VC, and FEV₁/FVC) and DLCO
- Use of augmentation treatment at any time throughout the study
- Time from baseline to initiation of augmentation therapy
- Number and severity of chronic obstructive pulmonary disease (COPD)
 exacerbations based on Global Initiative for Chronic Obstructive Lung Disease
 (GOLD) criteria in active versus placebo will be evaluated as an AE of special
 interest

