FSH (post-menopausal females)	X										patier						
Clinical Labs (heme, coag, trop, chem, lipids, urinalysis) ⁴	Х		Pre-dose X	Х	х	Pre-dose X	х	х	Pre-dose X	Х	until last patient with fibrosis	Pre-dose X		х		х	х
PRO-C3/PRO-C6	X								X		brosi	Pre-dose X		X		x	x
Calculate APRI			Pre-dose X						Pre-dose X		receives	Pre-dose X (Weeks 40, 64, 88, 112, 136, and 160)		х		х	х
Anti-drug Antibodies	X		Pre-dose X			Pre-dose X			Pre-dose X		10 th dose	Pre-dose X				X	х
Z-AAT Level	X		Pre-dose X		X	Pre-dose X		X	Pre-dose X		se (W	Pre-dose X		х		Х	х
Serum Alpha-1 Antitrypsin Level	X		Pre-dose X		X	Pre-dose X		X	Pre-dose X		(Week 100)	Pre-dose X		х		Х	Х
Concomitant Meds/Therapies	X		X	х	X	X	Х	X	X	X	ē	х		х		Х	x
Adverse Events	X		X	X	X	X	X	X	X	X		X		X		X	X
Study Treatment			X			X			X			X					
Pharmacokinetics (PK)			Pre-dose, 1 hr, & 2 hr post-dose X	X					Pre-dose, 1 hr, & 2 hr post-dose X	X							
Phone Call to Assess AEs													X				
Phone Call to Assess for Pregnancy Post-dose															Х		

- 1. Pulmonary function testing includes: Spirometry including VC, FVC, FEV₁, FEV₁/VC, FEV₁/FVC, and DLCO. Pertinent study FEV₁ will be based on post-bronchodilation value. Spirometry testing at Screening is to determine inclusion/exclusion. Spirometry and DLCO may be repeated once per timepoint. Spirometry and DLCO should also be conducted any time a patient experiences a COPD exacerbation. For dosing visits between Week 28 and Week 196, DLCO can occur once every 6 months.
- 2. MRI hepatoscan will include magnetic resonance elastography (MRE), hepatic fat content by MRI-PDFF (or equivalent) and hepatic iron content. MRI should always be completed before biopsy (if performed on the same day) and after a 4-hour fast from food.
- 3. A complete physical exam (PE) is to be performed at Screening and Study Completion/Early Termination. A symptom-directed PE is to be performed at all other designated visits. Genitourinary exam may be deferred.
- 4. Patients should be fasting (water only) for a minimum of 2 hours prior to collection of the clinical labs.
- 5. A post-dose biopsy visit will occur at Week 48 (± 2 weeks) for patients with evidence of fibrosis at Screening. For patients beyond Week 48 at the time of IRB/EC approval of Protocol v4.0, the post-dose liver biopsy will be performed at Week 72 (± 4 weeks) or Week 96 (± 4 weeks).
- 6. The Study Completion visit can occur 4 to 12 weeks from the last study dose.

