The AROAAT2001 design and conduct is supported by existing nonclinical pharmacology and toxicology data as well as data from a Phase 1 clinical study AROAAT1001 in healthy volunteers which evaluated safety, PK, and PD effect of single and multiple escalating doses of fazirsiran. AATD patients with AATD associated liver disease will require multiple doses of fazirsiran to sustain hepatic silencing of AAT production. Accordingly, this study uses multiple doses of fazirsiran with each dose after the second dose administered approximately every 3 months.

Three different dose levels are being tested. The dosing regimen utilized in this study is supported by the PD effect and safety profile of three once every 28 days (Q28) doses of fazirsiran, which was evaluated in the AROAAT1001 study. Single dose PD effect from the AROAAT1001 study indicates that AAT serum protein levels generally reach nadir, but not always full suppression to below lower limit of quantitation around Week 6 to 8 and start to rebound by approximately Week 12 after a single dose. This observed time until rebound supports quarterly dosing. This study also demonstrated that a second dose at Day 29 (4 weeks after initial dose) resulted in complete suppression of circulating AAT levels that was sustained. (See Investigator's Brochure for details.) Based on these results, it was determined that 2 doses administered 28 days apart would quickly lead to maximal and sustained reduction in hepatic AAT production but thereafter dosing could be quarterly. Hence, this was viewed as the best approach to achieve the fullest level of hepatic reduction of the insulting agent while minimizing overall patient exposure by moving to quarterly dosing.

Based on non-clinical studies in the PiZ mouse model and experience with liver recovery from other necro-inflammatory diseases such as viral hepatitis, it is highly likely that dose administration beyond 3 doses will be required to reduce insoluble aggregated liver Z-AAT sufficiently to reduce globule inflammation and hopefully allow repair of hepatic architecture. Based on other precedents as discussed above, improvement of fibrosis or other adverse liver histologic findings due to AATD liver disease may require long-term therapy to show improvement.

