9. STUDY METHODS AND SCHEDULES

9.1. Overview of Procedures

Patients will undergo the following evaluations at regular intervals during the study (refer to the SOA): medical history, physical examinations, vital sign measurements (BP, temperature, heart rate, respiratory rate), weight (at baseline), AE monitoring, ECGs, urine pregnancy test/FSH (females), concurrent medication, pulmonary function testing (spirometry including VC, FVC, FEV₁/FVC, FEV₁/FVC, and DLCO) and sample collection for hematology, coagulation, biochemistry, lipids, cardiac troponin, urinalysis, urine cotinine, anti-drug antibodies, drug screens, serum alpha-1 antitrypsin levels (where applicable), serum fibrosis biomarkers, liver biopsy, MRI (where feasible and available), and FibroScan® (where available).

Evaluations during Screening should be completed in the following order (if feasible):

Within Day -60 to Day -1 Screening window: MRI and FibroScan®, followed by liver biopsy

Within Day -30 to Day -1 Screening window: PFTs

Study visits will occur during the Screening window (Days -60 to -1), and as per the SOA. The exception is pulmonary function testing, which must be done within the Day -30 to Day 1 Screening window.

Eligible patients will attend the Clinical Facility on Day 1. Note that study dose administration is on Day 1, which must occur within 60 days of Screening.

On arrival at the clinical facility on Day 1, the Investigator, or designee, will meet with patients to reiterate all study procedures and encourage patients to ask any questions. Patients will fast from food for at least 2 hours pre-dose. Refer to the SOA for additional information. Patients will be confined to the clinical facility for approximately 4 hours on dosing days.

The Investigator (or medically qualified designee) will be required to remain within the clinical study facility for 2 hours after dosing on Day 1 and will remain on call for the duration of the study. Patients should refrain from strenuous physical activities, beyond their normal fitness level, throughout the study.

Clinically significant changes including AEs will be followed until resolution is achieved, or until medically stable or the event is otherwise explained, or until the patient is lost to follow-up. A telephone follow-up will occur 90 days after the last dose to assess for pregnancy occurrence.

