9.3.10. Follow-Up Procedures: Telephone Call to Assess for Adverse Events

Documented telephone contact with each patient to verify the following:

Adverse Events and Concomitant Medications: 24 to 48 hours after the following doses:

Any dose given after Week 16 (Day 113)

Compliance with contraceptive measures and absence of any known pregnancy:

90 days after the last dose of study treatment

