10.3. Timing, Frequency, and Method of Detecting AEs

Any pre-existing conditions or signs and/or symptoms present in a patient prior to the start of the study (i.e., before informed consent) should be recorded as Medical/Surgical History.

All AEs occurring after informed consent and on or before the final visit must be reported as AEs; only AEs that occur post-dose will be considered treatment-emergent. All AEs must be recorded irrespective of whether they are considered drug-related.

At each visit/assessment in the period defined above, AEs will be evaluated by the Investigator (or medically qualified designee) and recorded in the medical notes and eCRF.

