10.9. Post-study AEs

A post-study AE is defined as any event that occurs outside of the AE detection period defined in Section 10.3.

Investigators are not obligated to actively seek AEs in former study patients. However, if the Investigator learns of any SAE, including a death, at any time after a patient has been discharged from the study, and he/she considers the event reasonably related to the investigational product, the Investigator will promptly notify Arrowhead.

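### The open-label exposure-adjusted AE rate counts events to end of study but person-time only to the last dose; as an optional extra, the 90-day call could also ask about AEs

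*Protocol*

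**What the plan says.** **The rate.** SAP addendum Section 4, Table 1 defines an open-label treatment-emergent AE as one that starts or worsens after the first open-label dose, up to end of study or Early Termination. Section 6.4.1 defines the exposure-adjusted rate as the number of subjects with the event divided by summed exposure. Each subject's exposure is the last dose date minus the first dose date of study drug, plus one day, in years.

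**The end of follow-up.** For patients with fibrosis, Protocol Table 2, footnote 6 states: "The Study Completion visit can occur 4 to 12 weeks from the last study dose". Protocol 10.3 sets the reporting period: "All AEs occurring after informed consent and on or before the final visit must be reported as AEs". After that, Protocol 10.9 applies: "Investigators are not obligated to actively seek AEs in former study patients".

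**The later call.** The Synopsis lists a "90-day, post-last dose follow-up phone call to assess for pregnancy occurrence", and Protocol 9.1 says the same. Protocol 9.3.10 gives its content: "Compliance with contraceptive measures and absence of any known pregnancy". The Adverse Events row of Table 2 has no mark in the 90-day column.

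**The concern.** A rate needs its events and its person-time to cover the same period. Here events count for 4 to 12 weeks longer than time does. The size of the error depends on where in that window each completion visit falls and on how many open-label doses the patient had; neither has to do with the drug. The formula also refers to study drug in general, so it does not say outright whether the clock starts at the first open-label dose or at Day 1.

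The stake is modest. Protocol 6.2 gives long-term safety as the purpose of the open-label phase, and these rates are one descriptive summary of it. The primary endpoint and the comparisons with placebo are not touched.

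A second, smaller point is that routine seeking of new AEs may stop 28 days after the last dose. A required contact about two months later does not ask about them.

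**Working it through.** **Check of the schedule.** 8 weeks of screening + 196 weeks of dosing + 12 weeks = 216 weeks, the protocol's stated maximum. Doses on Day 1, at Weeks 4 and 16, and then every 12 weeks to Week 196 make 18 doses, the tenth at Week 100, as stated.

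**Inputs.** The completion visit is 28 to 84 days after the last dose (Table 2, footnote 6). Two assumptions are needed. End of study is taken as the Study Completion visit. The first open-label dose is taken as the first scheduled dose after the biopsy, so Week 52, 76 or 100 after a biopsy at Week 48, 72 or 96.

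**Formulas.** Exposure D = 7 × (last week − first week) + 1 days. Event window W = D + 28 to D + 84. The numerator is the same either way, so the planned rate is W/D times the rate computed over the event window.

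| Open-label doses | D (days) | W (days) | W/D |
|---|---|---|---|
| Weeks 52 to 100 | 337 | 365 to 421 | 1.08 to 1.25 |
| Weeks 52 to 196 | 1009 | 1037 to 1093 | 1.03 to 1.08 |
| Weeks 76 to 100 | 169 | 197 to 253 | 1.17 to 1.50 |
| One dose only | 1 | 29 to 85 | not useful |

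If the first day is left out of W, the third row becomes 196/169 = 1.16 to 252/169 = 1.49; the first two rows do not change at two decimals. Exposure is summed over subjects, so one patient with a single dose does not distort the rate alone, but contributes 1 day of time against 29 to 85 days of event counting.

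**Clock started at Day 1 instead.** For a last dose at Week 100, D = 701 days and W is unchanged for an open-label start at Week 52: 365/701 = 0.52 to 421/701 = 0.60. The mismatch reverses.

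**Counting each subject once.** The formula keeps adding time after a subject has had the event, although that subject cannot be counted again. With a constant hazard and a proportion p of subjects affected by the end of W, subjects/W is p/[−ln(1 − p)] of the hazard: 0.30/0.357 = 0.84 for p = 0.30 and 0.60/0.916 = 0.65 for p = 0.60. For Weeks 52 to 100 and p = 0.30, the planned rate is 1.083 × 0.841 = 0.91 to 1.249 × 0.841 = 1.05 of the hazard. The two errors pull in opposite directions. The overstatement in the table applies in full only to rare terms.

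**The gap before the call.** The call is at day 90 ± 5. With completion at Week 4: 85 − 28 = 57 to 95 − 28 = 67 days. With completion at Week 12: 85 − 84 = 1 to 95 − 84 = 11 days.

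**The case against.** *The table is descriptive, and SAPv3.0 may define exposure.* The first part is true and limits the importance. SAPv3.0 is not among the documents, but Section 6.4.1 states its own formula, and that formula does not match the addendum's own event window.

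*The Day 1 reading is strained.* It is. The addendum concerns the open-label phase and anchors baseline, study day and treatment-emergence to the first open-label dose. That is the natural reading here too, but the wording should say so.

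*The largest ratios are corner cases.* Partly. Patients with a Week 72 or 96 biopsy were already beyond Week 48 when Protocol v4.0 was approved, so many may be dosed past Week 100 unless an extension opens at their site. The mix of dosing lengths is not given.

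*Follow-up after the last dose is adequate already.* Safeguards do exist. Open AEs are followed (Protocol 10.6), related serious events that the site learns of are reported (10.9), and Appendix 3 adds monitoring after a confirmed lung-function decline. None of them seeks new non-serious events, but safety reporting does not simply stop. With completion at Week 12 almost no gap remains.

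A reader might infer three stronger points that the documents do not support:

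- **That collection stops before the drug's maximum effect.** Protocol 4.7 says "AAT serum protein levels generally reach nadir, but not always full suppression to below lower limit of quantitation around Week 6 to 8", but this describes a single dose in healthy volunteers. The same section reports complete, sustained suppression after a second dose at Day 29. Patients stopped by the last-patient rule have had at least ten doses.
- **That the COPD comparison is weakened.** COPD exacerbation is of special interest as active versus placebo. In the open-label phase every patient receives 200 mg.
- **That 4.1 person-years is the most that can be lost.** 24 × 62/365.25 = 4.1, but 24 is the planned minimum with fibrosis, and a 67-day gap gives 24 × 67/365.25 = 4.4. Entry into the extension lowers the figure by an unknown amount.

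**Conclusion.** The rate is wrong as written, because its denominator ends 28 to 84 days before its numerator does. On the natural reading the event window exceeds exposure by 8% to 25% for Weeks 52 to 100, by 3% to 8% for Weeks 52 to 196, and by about 16% to 50% for Weeks 76 to 100. These figures assume open-label dosing starts at the first scheduled dose after the biopsy, and they apply to patients who reach the completion visit. For common terms, time counted after the first event works the other way, so the net direction depends on the term. Only descriptive open-label rates are affected.

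The follow-up point is an optional improvement. Its rationale is complete descriptive safety data over the last 12-week dosing interval. The number of AEs missed cannot be derived from the documents.

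**What to change.** **Recommended.** In SAP addendum Section 6.4.1, start each subject's time at the first open-label dose and end it on the date the treatment-emergent window ends (end of study or Early Termination). For each preferred term, stop the subject's time at its first occurrence. Both changes are needed: matching the dates alone leaves rates of common terms too low. The cost is a sentence or two and minor programming.

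**Optional.** For patients with fibrosis who do not enter the extension, add questions on AEs, COPD exacerbations and new augmentation therapy to the 90-day call. Extend the AE window and the person-time to that call. If the person-time were left at the planned formula, the Weeks 52 to 100 ratio would become (336 + 90 + 1)/337 = 1.27. State whether the spirometry and DLCO required at an exacerbation apply to one first reported at the call. The 4-to-12-week completion window can stay, and no new contact is scheduled. The cost is a protocol amendment with IRB/EC approval, possible unscheduled lung-function tests, and final AE data about two months later if the last patient completes at Week 4.

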3. LIST OF ABBREVIATIONS AND TERMS

AAT Alpha-1 antitrypsin

AATD Alpha-1 antitrypsin deficiency

ADA Anti-drug antibody

ADS-001 Drug substance (API, lyophilized powder) containing RNAi trigger

(also referred to as fazirsiran, ARO-AAT, or TAK-999)

AE Adverse event

ALP Alkaline phosphatase ALT Alanine aminotransferase

API Active Pharmaceutical Ingredient

APRI Aspartate aminotransferase-to-platelet ratio index

ARC-AAT Arrowhead previous clinical stage RNAi therapeutic candidate for

AATD; discontinued

ARO Arrowhead Pharmaceuticals, Inc
ARO-AAT Short name for ARO-AAT Injection

ARO-AAT Injection Clinical drug product solution ready for SC injection (also referred

to as Fazirsiran Injection or TAK-999 Injection)

AST Aspartate aminotransferase

BMI Body mass index BP Blood pressure

cGCP Current Good Clinical Practice

cGMP Current Good Manufacturing Practice
COPD Chronic obstructive pulmonary disease

CRA Clinical Research Associate
CRO Contract Research Organization

CS Clinically significant
CTN Clinical Trial Notification
CV Coefficient of variation
CVA Cerebrovascular accident

DLCO Diffusing capacity for carbon monoxide

DSMB Data Safety Monitoring Board

EC Ethics Committee ECG Electrocardiogram

eCRF Electronic Case Report Form eGFR Estimated glomerular filtration rate

EOS End of Study
FAS Full Analysis Set

Fazirsiran Drug substance (API, lyophilized powder) containing RNAi trigger

(also referred to as ADS-001, ARO-AAT, or TAK-999)

Fazirsiran Injection Clinical drug product solution ready for subcutaneous injection (also

referred to as ARO-AAT Injection or TAK-999 Injection)

FDA Food and Drug Administration

FEV₁ Forced expiratory volume in one second

Arrowhead Pharmaceuticals, Inc.

Protocol No.: AROAAT2001

FEV₁/FVC Ratio of the forced expiratory volume in the first one second to the

forced vital capacity of the lungs

FEV₁/VC Ratio of the forced expiratory volume in 1 second to vital capacity

FIB-4 Fibrosis-4 index

FSH Follicle-stimulating hormone

FVC Forced vital capacity
GCP Good Clinical Practice
GGT Gamma glutamyl transferase

GLP Good Laboratory Practice

GOLD Global Initiative for Chronic Obstructive Lung Disease

HBV Hepatitis B virus HCV Hepatitis C virus

HDL High-density lipoprotein

HIV Human immunodeficiency virus

HR Heart rate

ICH International Council for Harmonisation

INR International normalized ratio
IRB Institutional Review Board
ISR Injection site reaction

IUD Intrauterine device

IWRS Interactive Web Response System

LD Lactate dehydrogenase
LDL Low-density lipoprotein
MAR Missing at random
MCH Mean cell hemoglobin

MCHC Mean cell hemoglobin concentration

MCV Mean cell volume
MI Multiple imputation
mmHg Millimeters of mercury
MNAR Missing Not at Random

MRE Magnetic resonance elastography
MRI Magnetic resonance imaging

MRI-PDFF Magnetic resonance imaging proton density fat fraction

mRNA Messenger RNA

NAFLD Nonalcoholic fatty liver disease NASH Nonalcoholic steatohepatitis

NHP Non-human primate

NOAEL No-observed-adverse-effect level NSAID Nonsteroidal anti-inflammatory drug

PBO Placebo

PD Pharmacodynamic
PFT Pulmonary function test
PI Principal Investigator

PiZZ Homozygous Z allele individuals

Arrowhead Pharmaceuticals, Inc.

Protocol No.: AROAAT2001

PK Pharmacokinetic(s)
PT Preferred Term

PTT Partial thromboplastin time

Q28 Once every 28 days Q4W Once every 4 weeks

QT QT interval - a measure of the time between the start of the Q wave

and the end of the T wave in the heart's electrical cycle

RBC Red blood cell
RNAi RNA interference
RR Respiratory rate
SAE Serious adverse event
SAP Statistical Analysis Plan
SD Standard deviation

siRNA Small interfering RNA oligonucleotides

SOA Schedule of Assessments
TIA Transient ischemic attack
ULN Upper limit of normal

VC Vital capacity

WOCBP Women of childbearing potential Z-AAT Mutant AAT protein from Z allele

4. INTRODUCTION

4.1. Background Information

Alpha-1 antitrypsin deficiency is an autosomal co-dominant genetic disorder with a prevalence range of 1/1500-1/5000 that causes early pulmonary disease in adults and liver disease in children and adults (Nelson et al., 2012). Alpha-1-antitrypsin (AAT) is a 52 kDa circulating glycoprotein protease inhibitor of the serpin family. The primary function of AAT is to inhibit neutrophil elastase to prevent excessive elastase-induced tissue damage. Normally, AAT is synthesized primarily in hepatocytes and several grams daily are secreted directly into the serum. In lung parenchyma, AAT is critical for protection of alveolar interstitial elastin from degradation by neutrophil elastase. A lack of adequate levels of functional AAT leads to damage of lung elastin by neutrophil elastase and the development of early emphysema. It generally takes decades for lung disease to manifest and usually requires additional environmental insult, usually cigarette smoking. Low plasma AAT levels that lead to pulmonary disease in individuals homozygous for the Z mutation (PiZZ) are not from a lack of synthesis (except in null/null patients) but from a disruption of its processing and secretion by hepatocytes. AAT is normally secreted in monomeric form, but the mutant AAT protein from Z allele (Z-AAT) synthesized by PiZZ individuals contains a single point mutation that results in low secretion, polymer formation and accumulation in hepatocytes leading to liver disease. Lung disease is frequently treated with AAT replacement therapy, and fewer than 10,000 patients are on replacement or "augmentation" therapy in the U.S. (Stoller et al., 2012). However, augmentation therapy does nothing to treat liver disease, and no specific therapy is available for alpha-1 antitrypsin deficiency (AATD)-associated liver disease.

In clinical practice, over 90% of AAT deficiency is due to the PiZZ genotype (De Serres et al., 2012). PiZZ adult patients may initially present with clinical signs of pulmonary disease such as dyspnea, cough, or chronic bronchitis, or they may initially present with signs of liver disease such as elevated transaminases or bilirubin, hepatitis, or cirrhosis (American Thoracic Society/European Respiratory Society 2003). Pediatric patients typically present with clinical symptoms of liver disease, which may include asymptomatic chronic hepatitis, failure to thrive, poor feeding, or hepatomegaly and splenomegaly. However, disease natural history in both pediatric and adult patients is variable.

A 2018 publication by Clark et al., examined 94 PiZZ adults using liver biopsy and various other noninvasive measures of liver disease (e.g., transient elastography, Fibrosis-4 index [FIB-4]) (Clark et al., 2018). In this cohort, the prevalence of clinically significant liver disease (≥F2) was 35.1%. The presence of accumulated Z-AAT globules, portal inflammation, and hepatocellular degeneration were associated with clinically significant fibrosis. Similarly, accumulation of Z-AAT globules, portal inflammation, and hepatocellular degeneration are seen on histologic evaluation of the PiZ mouse model liver.

